2 INVESTIGATIONAL DEVICE

2.1 Device Summary

This chapter contains a summary description of the **investigational device** and its intended purpose.

Summary device description
	
Philips IntelliSpace Cognition (ISC) is a digital proposition from the Digital Cognitive Diagnostics (DCDx) venture. It is a digital aid which supports HealthCare Professionals (HCPs) in assessing the cognition of individuals within a healthcare facility. It consists of two interfaces connected to the DCDx-module in the cloud. ISC will be hosted on the Health Suite Digital Platform (HSDP). The first interface is the patient’s interface and is presented via a tablet to collect data on how the patient performs a series of tests. The second interface is the clinician’s interface and is typically located on a laptop. It allows for tests or test batteries to be selected, observations noted, data analytics performed and the generation of a report. Philips ISC is a Class-II Medical Device in the US and provides objective data regarding cognition via scoring algorithms that HCPs can use to inform diagnostic decision making and treatment planning. It enables tracking cognition over time and offers the possibility of new outcome measures. ISC can be used in a variety of healthcare environments such as neurology and neuropsychology practices.
 
In this study 4 devices/tools will be used:
 
 
• A version of the ISC medical product (as engineered in accordance with the HealthWorks QMS) and that is verified to be used for data collection and provides the interface of the final product for the tests: TMT, Clock Drawing Test, MMSE-2, ROCFT, and Digit Span Test.
 
• A production equivalent (research platform) that provides: O Cancellation Test, Category Fluency Test, RAVLT, COWAT and Star Cancellation.
 
• Paper tests: Trail Making Test, Rey Osterrieth Complex Figure Test, Digit Span Test, Controlled Oral Word Association Test, Category Fluency Test, Rey Auditory Verbal Learning Test, Clock Drawing Test, Star Cancellation Test, O Cancellation Test, MMSE-2. In addition a naming test in paper format will also be included.
 
• A MoCA paper based screener test.
 
 
In this study, these devices/tools will be used to investigate score distributions, construct validity and test-retest reliability.


Summary intended purpose
	
The IntelliSpace Cognition tool is intended to be used as an adjunctive tool in the assessment of an adults’ level of cognitive functioning.
 
The IntelliSpace Cognition tool provides health care professionals with an overview of both the overall cognitive performance as well as specific cognitive domains.
 
The IntelliSpace Cognition tool provides health care professionals with a method to compare a person’s cognitive performance over different assessments (moments in time).

Title: Clinical Investigation Plan		Author: [name]		Company Restricted	
DocID: ICBE-2-28674	Version: 2.0	Date: 2019-02-18	Status: Approved	Page: 14 of 35	
IRBMANAGER PILOT – QI PROJECT					

	
The results from IntelliSpace Cognition tool are intended to be used by healthcare professionals who have participated in IntelliSpace Cognition trainings.
 
The data collected by IntelliSpace Cognition are intended to be collected under the supervision of a HCP.
 
The IntelliSpace Cognition tool is not intended as a stand-alone or adjunctive diagnostic device.
 
The assessments provided via the IntelliSpace Cognition tool may be used for a wide variety of patient groups, as well as healthy individuals when a HCP wishes to gain more insight into cognitive performance.
 
Disclaimer:
 
 
• The cognitive model of IntelliSpace Cognition tool has been scientifically validated for assessing the cognition of healthy people in the age group of 55-80.
 
• The IntelliSpace Cognition tool has not been validated for use with adults under the age of 55 or over the age of 80 and doesn't include normative data for adults under the age of 50 or over the age of 80.
 

Population description	The tests provided via the IntelliSpace Cognition may be used for anyone where an overview of cognitive functioning is required provided they are part of the demographic group as described in the section titled "subjects".
Manufacturer	The legal manufacturer is Philips HealthWorks for which FDA 21 CFR 820.30 compliant design control will be implemented to allow for clinical validation of the device as part of 21 CFR 820.12 Investigational Device Exemptions.
Device model/type	
A released version of the ISC product (as engineered in accordance with the HealthWorks QMS) and that is verified to be used for data collection and provides the interface of the final product for the tests: TMT, Clock Drawing Test, MMSE-2, ROCFT and Digit Span Test.
 
A production equivalent (research platform) that provides: O Cancellation Test, Category Fluency Test, RAVLT, COWAT and the Star Cancellation.

Software version	
Software version 1.0.0 of the ISC product will be released for the clinical investigation.
 
Software version 3.10.6A of the product equivalent will be used for the clinical investigation.

Accessories	
iPad Pro tablets (Apple)
 
Apple pencils
 
Regular laptops

Traceability procedure	Maintenance of the device will be carried out by Philips employees. Cleaning of the device will be carried out as needed by the investigators. When the device is not used for the clinical investigation it is placed inside a locked cabinet in a locked office at the sites. At clinical investigation termination or

Title: Clinical Investigation Plan		Author: [name]		Company Restricted	
DocID: ICBE-2-28674	Version: 2.0	Date: 2019-02-18	Status: Approved	Page: 15 of 35	
IRBMANAGER PILOT – QI PROJECT					

	closure, the device will be returned to Philips and checked by the Monitor. The devices, SW and accessories are uniquely identified and listed in appendix B Validation ISC – device list.
Required training	Persons qualified to administer the neuropsychological tests, i.e. a psychologist or psychometrist, will use the investigational devices to collect data as part of the clinical investigation. Employees of Philips will train the researchers for operation of the investigational devices.
Specific procedure acts	N/A
Device Labeling	The software will contain a label with the text; not for clinical use.

### 2.2 Intended purpose

The IntelliSpace Cognition tool is intended to be used as an adjunctive tool in the assessment of an adults' level of cognitive functioning.

The IntelliSpace Cognition tool provides health care professionals with an overview of both the overall cognitive performance as well as specific cognitive domains

The IntelliSpace Cognition tool provides health care professionals with a method to compare a person's cognitive performance over different assessments (moments in time).

The results from IntelliSpace Cognition tool are intended to be used by healthcare professionals who have participated in IntelliSpace Cognition trainings.

The data collected by IntelliSpace Cognition are intended to be collected under the supervision of a HCP

The IntelliSpace Cognition tool is not intended as a stand-alone or adjunctive diagnostic device.

The assessments provided via the IntelliSpace Cognition tool may be used for a wide variety of patient groups, as well as healthy individuals when a HCP wishes to gain more insight into cognitive performance.

Disclaimer:

- The cognitive model of IntelliSpace Cognition tool has been scientifically validated for assessing the cognition of healthy people in the age group of 55-80
- The IntelliSpace Cognition tool has not been validated for use with adults under the age of 55 or over the age of 80 and doesn't include normative data for adults under the age of 50 or over the age of 80.

### 2.3 Device Description

Philips IntelliSpace Cognition (ISC) is a digital proposition from the Digital Cognitive Diagnostics (DCDx) venture. It is a digital aid which supports HealthCare Professionals (HCPs) in assessing the cognition of individuals within a healthcare facility. It consists of two interfaces connected to the DCDx-module in the cloud. ISC will be hosted on the Health Suite Digital Platform (HSDP). The first interface is the patient's interface and is presented via a tablet to collect data on how the patient performs a series of tests. The second interface is the clinician's interface and is typically located on a laptop. It

Title: Clinical Investigation Plan		Author: [name]		Company Restricted	
DocID: ICBE-2-28674	Version: 2.0	Date: 2019-02-18	Status: Approved	Page: 16 of 35	
IRBMANAGER PILOT – QI PROJECT					

allows for tests or test batteries to be selected, observations noted, data analytics performed and the generation of a report. Philips ISC is a Class-II Medical Device in the US and provides objective data regarding cognition via scoring algorithms that HCPs can use to inform diagnostic decision making and treatment planning. It enables tracking cognition over time and offers the possibility of new outcome measures. ISC can be used in a variety of healthcare environments such as neurology and neuropsychology practices.

In this study 4 devices/tools will be used:

- A version of the ISC medical product (as engineered in accordance with the HealthWorks QMS) and that is verified to be used for data collection and provides the interface of the final product for the tests: TMT, Clock Drawing Test, MMSE-2, ROCFT, and Digit Span Test.
- A production equivalent (research platform) that provides: O Cancellation Test, Category Fluency Test, RAVLT, COWAT and Star Cancellation.
- Paper tests: Trail Making Test, Rey Osterrieth Complex Figure Test, Digit Span Test, Controlled Oral Word Association Test, Category Fluency Test, Rey Auditory Verbal Learning Test, Clock Drawing Test, Star Cancellation Test, O Cancellation Test, MMSE-2. In addition a naming test in paper format will also be included.
- A MoCA paper based screener test.

In this study, these devices/tools will be used to investigate score distributions, construct validity and test-retest reliability.

The ISC production equivalent that will be used for administering O Cancellation Test, Category Fluency Test, RAVLT, COWAT and Star Cancellation has the exact same patient interface as the end-product. The digital tests will be provided to the participants on an iPad Pro tablet (Apple). It has a screen size of 12.9-inches with a screen resolution of 2732x2048. This is the exact same tablet as required for use of the final ISC product.

Participants will use the Apple pencil for the iPad Pro tablet to perform the digital tests (see Figure 1). The tablet will present instructions for each test to participants via both written text and audio recordings. A researcher will observe in order to ensure that the participant understands and follows the instructions (see Figure 2). The iPad Pro tablet, Apple pencil and the regular laptop, which may be used by the researcher to take notes, are all CE marked devices.

Figure 1. iPad pro and Apple pencil used by the participant

Figure 2. Regular laptop used by researcher

The ISC production equivalent and ISC product (verified for data collection, SW version 1.0.0) are only utilized to collect data. The scoring algorithms for the ROCFT and the Clock Drawing Test have either not yet been implemented or the output of those that have been implemented will not be considered relevant. The data collected with the device during the clinical investigation will be used to assess the equivalence of outputs from automatic scoring by the algorithms to traditional manual scoring. Only when the output of the algorithms have high agreement with manual scores of the respective test, the algorithms will be integrated into the final ISC product.

### 3 JUSTIFICATION

While the ISC product may be used in a variety of situations the most likely is within a neurology office. The use-case for ISC is that the raw data are collected via the ipad under the supervision of an assistant.

Title: Clinical Investigation Plan		Author: [name]		Company Restricted	
DocID: ICBE-2-28674	Version: 2.0	Date: 2019-02-18	Status: Approved	Page: 17 of 35	
IRBMANAGER PILOT – QI PROJECT					

Subsequently, various algorithms are applied to score the individual tests. These scores are then fed into a cognitive model, resulting in easy-to-interpret cognitive domain scores. The domain scores are norm referenced by age, and optionally by gender, education, and ethnicity. The output of ISC is used by the neurologist to help him/her arrive at his/her diagnosis or for creating an optimal therapy plan. In the case of recurring visits the cognitive domain scores give the neurologist (or HCP) metrics to objectively assess change over time.

A USA neurologist will on average send 13% of his patients for a full neuropsychological assessment while in an ideal world he/she would like to send 36% (The MarkeTech Group, 2018). A common reason for not referring for a full assessment is the waiting time of 3-6 months (The MarkeTech Group, 2018). There is a clear unmet need for a solution that gives more information than a simple screener tool but within an actionable time-window, preferably during the patient visit. For the majority of patients, ISC doesn't replace the full neuropsychological assessment but instead helps triage patients so that people that need a full assessment can be quickly identified and fast tracked.

In current clinical practice, neurologists perform an MMSE or MoCA screener and occasionally a haphazard cognitive test such as a clock drawing or a simple word recall trial. In general the neurologist does not possess the skill (or time) to score tests and normative data are rarely used. Computerized cognitive assessment can alleviate issues with haphazard cognitive testing and allow more accurate cognitive assessments to be performed at the neurology office. Digitized cognitive tests have a number of important benefits compared to paper-pencil tests including norm scores at the level of cognitive domains, continuous norm scores over age, more standardized administration and scoring, dynamic presentation of the test content according to the abilities of the patient, more sensitive measurement of reaction time, additional and potentially more sensitive outcome measures, and the possibility to replay test performance (Bauer et al., 2012; Klaming & Vlaskamp, 2017; Miller & Barr, 2017; Schatz & Browndyke, 2002).

The heart of IntelliSpace Cognition is the cognitive model. The model is based on structural equation modelling, has its roots in published literature and knowledge gleaned from key opinion leaders in neuropsychology. This provided mappings between test measures and the specific cognitive domains. These mappings were fit to the data of 148 healthy individuals in an early stage pilot in the Netherlands, and showed excellent fit. Moreover, the cognitive domains specified by the model demonstrated sensitivity to impairment in 51 stroke patients and 48 TBI patients. The model is currently based on accepted test measures. In the future it may be possible to incorporate new (to be validated) outcome measures into the model and so make it more sensitive or reduce the number of tests needed. For example in current neuropsychological clinical practice, interpretation of TMT performance is mostly restricted to total completion time and errors. Other behaviours during TMT performance are likely to reveal additional information, primarily about executive functioning, but in the current paper-pencil based format of the test it is difficult or impossible to measure these behaviours. Research has already started to look into new outcome measures for the TMT that are possible with digital measurement such as inter-element variability and a separation of layout-related processes from executive processes on TMT B (Klaming & Vlaskamp, 2017). In addition, digital assessment enables more accurate measurement of total completion time and a more standardized assessment of errors during performance of the test.

Another example of a digital test is the digital administration of the ROCFT which provides a number of important benefits over paper-pencil administration. Probably most importantly, digital administration enables automatic scoring of the drawing which not only saves time in the scoring of the test, but moreover contributes to better standardization of scoring. Additionally, it will be possible to implement different scoring algorithms including both quantitative and qualitative scoring algorithms. In current neuropsychological clinical practice, formalized qualitative scoring is only rarely performed despite the fact that qualitative scoring provides additional information about the patient's cognitive functioning beyond the information provided by quantitative scoring (Akshoomoff & Stiles, 1995; Anderson, Anderson, & Garth, 2001; Bennett-Levy, 1984; Chiulli, Haaland, Larue, & Garry, 1995; Deckersbach et al., 2000; Hamby, Wilkins, & Barry, 1993; Shorr, Delis, & Massman, 1992). Besides automatic scoring which would save time and decrease variability in scoring for both qualitative and quantitative scoring systems, digital administration allows for the extraction of additional data such as touch/pencil pressure and speed which may provide additional information about the patient's cognitive functioning. The use

Title: Clinical Investigation Plan		Author: [name]		Company Restricted	
DocID: ICBE-2-28674	Version: 2.0	Date: 2019-02-18	Status: Approved	Page: 18 of 35	
IRBMANAGER PILOT – QI PROJECT					

of computerized neuropsychological assessment has been recommended (Bauer et al., 2012; Miller & Barr, 2017; Strauss, Sherman, & Spreen, 2006).

The ISC cognitive model is based on mappings between cognitive domains and established outcome measures from well known paper-pencil tests which have many years of validation. It is vital for the validity of the digital tests, the cognitive model and their subsequent use in clinical practice that the comparability between the digital tests on the ISC platform and the corresponding paper-pencil tests is shown. This study aims at investigating the comparability of the relevant digital and paper-pencil cognitive tests, establishing the psychometric properties of the digital cognitive tests and collecting normative data for the digital tests so that the digital tests and the cognitive model can be used in clinical practice. Normative data is data from a reference population that establishes a baseline distribution for a score or measurement, and against which other scores or measurements can be compared. For this objective, data subjects are informed on the data we collect and the possible re-use of this data, including by 3rd parties.

**4 RISKS AND BENEFITS ASSESSMENT**

I have created and uploaded a risk management summary matrix

I have created and uploaded a risk management plan

A summary overview of the risks and benefits of the investigational device and the clinical procedure applied in this clinical investigation are listed in the table below.

Anticipated clinical benefits	IntelliSpace Cognition is a digital tool to assess cognition in an efficient way. It replaces the paper workflow by a digital workflow in a healthcare facility.
Anticipated adverse device effects	There are no risks of any adverse event, mild or serious
Residual risks associated with investigational device [as identified in risk analysis report]	- No risk for participants -Data loss (risk for validity)
Risks associated with participation in clinical investigation	- Privacy breach when devices are stolen and the system is not being logged off - Fatigue during participation (risk is almost zero)
Possible interactions with concomitant medical treatments	There are no interactions with concomitant medical treatments
Steps that will be taken to control or mitigate risks	- Privacy breach when devices are stolen and the system is not being logged off → systems will be logged off and stored in a locked cabinet

Title: Clinical Investigation Plan		Author: [name]		Company Restricted	
DocID: ICBE-2-28674	Version: 2.0	Date: 2019-02-18	Status: Approved	Page: 19 of 35	
IRBMANAGER PILOT – QI PROJECT					

	- Fatigue during participation → protocol will include a short break to prevent fatigue
Risk-to-benefit rationale	
There are no substantial risks or potential risks possible in this trial for participants and there are no risk of any adverse event, mild or serious.
 
The benefits will be to be able to launch IntelliSpace Cognition and in short; speed up the cognitive access process in clinics with use of Artificial Intelligence, by replacing the paper based workflow by a digital one and it will better triage patients /subjects to which ones needs a more robust cognitive assessment with a neuropsychologist.
 
The benefits of the use of the investigational device outweigh the risks.

## 5 OBJECTIVES AND HYPOTHESES

This chapter describes the objectives and hypotheses of the clinical investigation, as well as the claims and intended performance of the investigational device to be verified, and the risks and anticipated adverse device effects to be assessed.

### Primary objective:

The study has four aims.

1. To compare the psychometrics of digital and paper-pencil cognitive tests. Score distributions, test-retest reliability, and construct validity of the following tests will be compared: Trail Making Test (TMT), Rey Osterrieth Complex Figure Test (ROCFT), Digit Span Test, Controlled Oral Word Association Test (COWAT), Category Fluency Test, Rey Auditory Verbal Learning Test (RAVLT), Clock Drawing Test, Star Cancellation Test, O Cancellation Test, Mini Mental Status Exam 2 (MMSE-2).
2. To assess the degree of agreement between the algorithm and manual scores for the digital Rey Osterrieth Complex Figure Test and Clock Drawing Test.
3. To estimate regression-based norms and reliable change indices.
4. To estimate factor loadings for a structural equation model describing cognition in terms of distinct cognitive domains.

### Secondary objective(s)

The secondary objective of the study is to explore usability aspects of IntelliSpace Cognition.

### Primary hypotheses

The following primary hypotheses will be tested in the study:

Aim 1.

- A. Digital and paper-pencil normed test scores are comparable. We consider the two versions of a test comparable when the digital normed score is on average within .3 sd of the paper normed score and the two normed scores correlate at least .6.
- B. Test-retest reliability of the digital tests is comparable to test-retest reliability of the paper-pencil tests. We consider the reliability to be comparable when we observe no significant difference in a z-test between the digital and the paper-pencil test-retest correlations.

Title: Clinical Investigation Plan		Author: [name]		Company Restricted	
DocID: ICBE-2-28674	Version: 2.0	Date: 2019-02-18	Status: Approved	Page: 20 of 35	
IRBMANAGER PILOT – QI PROJECT					

C. Construct validity of the digital tests is comparable to the construct validity of the paper-pencil tests. We consider construct validity to be comparable when confirmatory factor analysis yields the same factor structure for digital and paper-pencil tests.

Aim 2.

D. The score(s) provided by the ROCFT and Clock Drawing Test scoring algorithms on ISC are correlated highly (> .8) to the score provided by manual scoring for the same drawings.

Aims 3 & 4 have no accompanying hypotheses.

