Investigation procedures	
The study consists of two phases. All participants in phase 1 will be invited to participate in two assessments that will take place with a time interval of two weeks between the two time points to minimize retest effects. Participants (total <math>N = 400</math>) will be randomly assigned to one of the following groups:
 
 
- Group A (<math>n=100</math>) completes digital tests in phase 1 and paper-pencil tests in phase 2,
 
- Group B (<math>n=100</math>) completes paper-pencil tests in phase 1 and digital tests in phase 2,
 
- Group C (<math>n=50</math>) completes digital tests in both phases,
 
- Group D (<math>n=50</math>) completes paper-pencil tests in both phases,
 
- Group E (<math>n=100</math>) only completes digital tests in one phase (50% of group E will be enrolled in phase 1 and the other 50% of group E will be enrolled in phase 2).
 
 
If the timeline allows for it, up to 50 additional participants aged 50-54 will be included in group E to stretch the age range for the regression-based norms, making the group size up to <math>n=150</math> and the total sample size up to <math>N = 450</math>.
 
The data of group A and B are used to compare score distributions within-subjects.
 
The data from groups A-D (phase 1) are used to compare score distributions between-subjects (aim 1).

Title: Clinical Investigation Plan		Author: [name]		Company Restricted	
DocID: ICBE-2-28674	Version: 2.0	Date: 2019-02-18	Status: Approved	Page: 10 of 35	
IRBMANAGER PILOT – QI PROJECT					

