**6 CLINICAL INVESTIGATION DESIGN**

**6.1 General**

The study has a randomized, counterbalanced design and consists of two phases (see figure 1). We sample participants according to the sampling plan outlined below, to ensure representativeness of the sample. We will oversample by 20% to account for dropout or incomplete data (the *n*'s below represent the desired cell counts, after dropout).

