**Figure 1. Schematic overview of study design.**

Title: Clinical Investigation Plan		Author: [name]		Company Restricted	
DocID: ICBE-2-28674	Version: 2.0	Date: 2019-02-18	Status: Approved	Page: 21 of 35	
IRBMANAGER PILOT – QI PROJECT					

Group	A	B	C	D	E
n	100	100	50	50	100-150
Phase 1 tests	Digital	Paper-pencil	Digital	Paper-pencil	Digital
Phase 2 tests	Paper-pencil	Digital	Digital	Paper-pencil	

All participants of Group A-D in phase 1 will be invited to participate in two assessments that will take place with a time interval of four-five weeks between the two phases to minimize retest effects. Participants will be randomly assigned with minimization for demographic variables (to make sure that the groups do not differ in terms of gender, age, education level, and ethnicity) to one of the following groups:

- Group A ( $n=100$ ) completes digital tests in phase 1 and paper-pencil tests in phase 2,
- Group B ( $n=100$ ) completes paper-pencil tests in phase 1 and digital tests in phase 2,
- Group C ( $n=50$ ) completes digital tests in both phases,
- Group D ( $n=50$ ) completes paper-pencil tests in both phases,
- Group E ( $n=100-150$ ) only completes digital tests in one phase (50% of group E will be enrolled in phase 1 and the other 50% of group E will be enrolled in phase 2).

The data of group A and B are used to compare score distributions within-subjects

The data from groups A-D (phase 1) are used to compare score distributions between-subjects (aim 1).

The data of group C and D are used to assess and compare test-retest reliability (aim 1) and assess reliable change indices (aim 3).

The data of group A (phase 1), group C (phase 1) and group E are used to estimate regression based norms for the digital tests (aim 3), as well as to estimate factor loadings for the structural equation model (aim 4).

The data of group A (phase 1), group B (phase 1), group C (phase 1) and group D (phase 1) are used to compare construct validity (aim 1).

Participants will be randomized with minimization for demographic variables (gender, age, education level, ethnicity).

The purpose of adding the 100-150 participants in Group E is to increase the sample size of participants who completed the digital tests for the first time for the norm data to 250-300.

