## 7 STATISTICAL CONSIDERATIONS

**Statistical design, analyses and power considerations**

Below we describe the planned analyses for each aim and hypothesis. The tests are scored by two raters (with 30% overlap) and inter-rater agreement is assessed prior to proceeding with the following analyses. All correlations mentioned below are Pearson correlations. Retest correlations are corrected for the variability of the normative sample (Allen & Yen, 2002; Magnusson, 1967). Correlation between paper and pencil measures are corrected for measurement error (Padilla & Veprinsky, 2012). In our power analyses we assume an alpha of .05.

Title: Clinical Investigation Plan		Author: [name]		Company Restricted	
DocID: ICBE-2-28674	Version: 2.0	Date: 2019-02-18	Status: Approved	Page: 25 of 35	
IRBMANAGER PILOT – QI PROJECT					

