**Aim 1 comparison of psychometrics.**

Hypothesis A: Digital and paper-pencil test scores are comparable.

For each test, we will first compute age-only referenced scores for digital and paper-pencil version separately. Referenced scores are computed based on the regression based norms (procedure described below under aim 3) and are represented as z-scores indicating a participant's deviation from what would be expected based on the norm sample for a participant with identical demographic characteristics. We then compute the correlation between digital and paper-pencil referenced scores within participants in group A and B (which are the groups in which participants completed both digital and paper-pencil versions of the tests), which needs to be  $r > .6$  to be considered comparable. Our planned sample size allows us to detect a correlation of  $r > .2$  with 80% power. We also perform an equivalence test for each test, comparing the distribution of digital normed scores with paper-pencil normed scores, using a two-one-sided-t-test approach (TOST; Schuirmann, 1987), with equivalence bounds of  $\pm .3$  sd, which we have 99% power to detect. Our planned sample size would allow us to detect equivalence with bounds of at least  $\pm .21$  with 80% power.

Hypothesis B: Test-retest reliability is comparable.

Test-retest reliability will be tested by examining for each test the correlation between the digital tests in phase 1 and phase 2 (group C) and comparing this to the correlation between the paper-pencil tests in phase 1 and phase 2 (group D). High test-retest correlations are expected ( $r > 0.7$ ), except for the ROCFT copy condition, since the scores of this condition generally show a moderate ceiling effect. The planned sample size for group C and group D each yield 80% power to detect  $r > .37$ .

Hypothesis C: Construct validity is comparable.

Construct validity will be investigated by means of two confirmatory factor analyses (CFA), one for each group (digital vs. paper-pencil). We expect to see that the factor structure that fits the paper-pencil data (phase 1, group B & D) well, will also fit the digital data (phase 1, group A & C) well. Assuming that at most two variables per test are included in the CFA, the subject-to-variable ratio is near 10:1 for each CFA.

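### Hypothesis B concludes that retest reliability is comparable from a non-significant z-test with 50 per group, and the stated power (r > .37) belongs to a different test.

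*Combined protocol and SAP*

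**What the plan says.** Section 5 (Primary hypotheses, Aim 1, B) sets the decision rule: "We consider the reliability to be comparable when we observe no significant difference in a z-test between the digital and the paper-pencil test-retest correlations".

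Section 7 (Aim 1, Hypothesis B) compares, test by test, the phase 1 to phase 2 correlation in group C with that in group D. Section 6.1 gives the groups: "Group C ( $n=50$ ) completes digital tests in both phases" and "Group D ( $n=50$ ) completes paper-pencil tests in both phases". These counts are after dropout: "We will oversample by 20% to account for dropout or incomplete data". Section 7 expects retest correlations above 0.7, apart from the ROCFT copy condition, but does not make this a condition for passing.

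On power, section 7 states "The planned sample size for group C and group D each yield 80% power to detect" r > .37. The alpha comes from the opening of section 7: "In our power analyses we assume an alpha of .05". The entries on significance and power and on pass/fail criteria only point back to the text above them.

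The interval between the two assessments is given twice. The Executive Summary has them "with a time interval of two weeks between the two time points to minimize retest effects"; section 6.1 has them "with a time interval of four-five weeks between the two phases to minimize retest effects".

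**The concern.** A non-significant difference does not show that two reliabilities are similar. It may only show that the comparison was imprecise, and a rule of this kind is easier to satisfy with fewer participants. The power figure offers no reassurance, because it answers whether each retest correlation differs from zero. That was never in doubt for tests expected to retest above .7.

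The plan uses a suitable method elsewhere. Section 7 tests hypothesis A with two one-sided tests and bounds of ±.3 sd, and Aim 2 applies the same approach to Fisher-transformed correlations with bounds of ±.1. Hypothesis B has no bounds.

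At stake is claim 3 in section 5, that the digital tests have psychometrics similar to paper, for which retest reliability is one of three properties compared under Aim 1. The device is also meant to track a person over time, and groups C and D supply the data for the reliable change indices. A loss of reliability accepted as comparable bears directly on that use.

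**Working it through.** **Inputs.** From the documents: n = 50 in group C and in group D, after dropout (section 6.1); alpha .05 (section 7; sidedness not stated, two-sided taken here and one-sided also shown); stated detectable r > .37; expected r > 0.7. Assumed: true paper reliabilities of .70, .80 and .90 with lower digital values, and the ordinary Fisher z standard error on uncorrected correlations.

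**1. Reproducing r > .37.** One correlation against zero, n = 50, two-sided .05.
- Noncentral t, 48 df, noncentrality √50 · r/√(1 − r²): 80% power at r = .375, and 78.8% power at r = .37.
- Fisher z: tanh[(1.960 + 0.842)/√47] = tanh(.409) = .387.
- One-sided versions give .336 (noncentral t) and .348 (Fisher z).

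The stated figure is therefore the single-group test against zero, two-sided.

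**2. The test that decides hypothesis B.** Two independent correlations:
- SE of the Fisher z difference = √(1/47 + 1/47) = .206.
- Difference detectable with 80% power = (1.960 + 0.842) × .206 = .578 on the z scale.
- Digital r at that difference: tanh(atanh .70 − .578) = .28; tanh(atanh .80 − .578) = .48; tanh(atanh .90 − .578) = .71.
- Largest observed gap that still passes = 1.960 × .206 = .404 in z. An observed digital r of about .60 against paper .80, or .43 against .70, is at the edge of passing.

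**3. Chance of being declared comparable.** With Δ the difference in atanh values, P(pass) = Φ(1.96 − Δ/SE) − Φ(−1.96 − Δ/SE).

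| True paper r | True digital r | Δ | P(pass) |
|---|---|---|---|
| .70 | .60 | .174 | 86.5% |
| .70 | .50 | .318 | 66% |
| .70 | .40 | .444 | 42% |
| .80 | .70 | .231 | 80% |
| .80 | .60 | .405 | 50% |
| .80 | .50 | .549 | 24% |
| .90 | .80 | .374 | 56% |
| .90 | .70 | .605 | 16.5% |

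Simulation with 400,000 samples per scenario agrees within one percentage point. With a one-sided test, P(pass) = Φ(1.645 − Δ/SE): 54% for .70 against .50, and 37% for .80 against .60.

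**4. What 50 per group supports with a margin.** Non-inferiority, one-sided .05, equal true reliabilities. With Δm the margin on the z scale, power = Φ(Δm/SE − 1.645), and n per group for 80% power = 2[(1.645 + 0.842)/Δm]² + 3.

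| Paper r | Margin in r | Power at n = 50 | n per group for 80% |
|---|---|---|---|
| .70 | .20 | 46% | 126 |
| .70 | .10 | 21% | 411 |
| .80 | .20 | 63% | 79 |
| .80 | .10 | 30% | 235 |

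At n = 50 the lowest limit that can be excluded with 80% power when paper r = .80 is tanh(1.099 − 2.487 × .206) = .53, a margin of about .27.

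**The case against.** The strongest reply is that the pass rates rest on assumed reliabilities and that the rule works better against large losses. That is partly right: .80 against .50 passes 24% of the time and .90 against .70 passes 16.5%. In the .80 against .70 case the digital test sits at the level the plan expects, so a pass there is not plainly an error. The problem is greatest for drops of 0.10 to 0.20 at paper reliabilities of about .70 to .80, where 50% to 87% pass.

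The percentages are also approximate. The plan does not say whether the z-test is one- or two-sided, and section 7 corrects retest correlations for the variability of the normative sample without saying how this enters the standard error. A one-sided test lowers the pass rates but does not rescue the rule, and the correction supplies no margin.

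The weakness of small samples is bounded here, since 50 per group is a post-dropout target that each cell must meet before the study closes. The r > .37 statement is not false: it says openly that it applies to each group. It is simply not the power needed. Hypothesis B is one of three supports for claim 3, not the only one.

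Finally, a margin-based test is demanding at this sample size, as step 4 shows. That limits which remedy is practical; it does not justify inferring similarity from non-significance. The conflicting retest interval is a separate defect and adds nothing to the case against the decision rule.

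**Conclusion.** The concern holds, and the rule must be changed before hypothesis B is used to support a claim. The pass rule is non-significance alone, and the stated power is for one correlation against zero. With 50 per group the actual comparison has 80% power only for falls such as .80 to .48 or .70 to .28. A true drop of 0.20 passes about 66% of the time at paper r = .70 and 50% at .80. These rates assume the listed true correlations, a two-sided .05 test and the uncorrected Fisher standard error; the flaw in the rule depends on none of them. The retest interval to which these correlations refer is also contradictory within the document.

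**What to change.** 1. Replace the rule for hypothesis B with a one-sided non-inferiority test, or an equivalence test, on the Fisher z difference with a margin fixed and justified in advance. An alternative is to require the lower confidence limit of the digital reliability to exceed a stated floor. In either case report the confidence interval of the difference, and say whether corrected or uncorrected correlations enter the test and with what standard error.
2. Remove the r > .37 statement and state what 50 + 50 delivers: a two-sided detectable difference of about .80 against .48, and a one-sided non-inferiority limit of about .53 when paper r = .80, both at 80% power.
3. If that margin is too wide to be useful, report both retest correlations and their difference with confidence intervals, and do not declare comparability.
4. Reconcile the Executive Summary and section 6.1 to a single retest interval.

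The cost is wording in sections 5 and 7, plus the interval correction; no added participants are needed for option 3 or for a wide margin. A .20 margin at 80% power would need about 79 to 126 per retest group, so a sponsor wanting that would have to enlarge groups C and D. The reliability claim becomes harder to make, and the stated power will look less favourable.
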